5. STUDY OUTCOMES

(ICH/E6 6.4.1; AGEK 4.1; SPIRIT #12)

ICH: A specific statement of the primary endpoints and the secondary endpoints, if any, to be measured during the trial.

This section includes a description of the overall, primary and secondary objective(s) of the study including the specific measurement variable and analysis metric.

	Assessment of the real-ear performance of hearing aids	Real-Ear Measurement (REM) [24]	Frequency Response [magnitude and phase of the output as a function of frequency]
	Determination of individual information or circumstances regarding hearing system and/or listening situation	Interviews: Qualitative and Quantitative (ad hoc list of questions, semi-standardized, standardized or normed), Focus Groups [29]	Narrative, open/closed replies, ranking, single/multiple choice, or point on a rating scale
	Quantitative assessment of a person's perception of facts or circumstances regarding hearing system	Semantic Differential Analysis/ Polarity Profile [25]	Point on a scale
	Determination of a present tinnitus	Tinnitus Pitch and Loudness Matching [26]	Tinnitus frequency/pitch [Hz] and sensation level [dB SL].
	Assessment of a person's perception of a specific listening situation through selected hearing systems or hearing aid programs	Simulations of Various Listening Situations (in Car/Cafeteria/Reverberation) via Loudspeakers including Preference Rating or Subjective Rating Scale	Preference or point on a scale
	Determination of localization capabilities with and/or without hearing systems	Localization Test in Quiet, Noise, Reverberation. [27]	Average RMS localization error [°], back-front confusions [%]
	Determination of dead regions in the cochlear	TEN (Threshold-Equalizing-Noise) Test [28]	Detection of pure tones presented simultaneously with a wide band noise (TEN) which produces the same level of masking [dB NPS] throughout audiogram frequencies (250 – 10k Hz)
	Assessment of a hearing aid user's affection by objective occlusion (closed ear canals)	Occlusion Measurement and Leakage Measurement using REM method [36]	Frequency Responses [magnitude and phase of the output as a function of frequency] => Level differences [dB] and Level Loss [dB]
	Assessment of real-time individual information regarding	MobEval [33, 34, 35]	Logging of predefined HI parameters, time [h/min/s],

	hearing system and/or listening situation via Phonak App on Smartphone in daily life		open/closed replies or single/multiple choice
Other	Assessment of third-party disability and the role of social support in hearing care	Quantitative Data through Questionnaires (e.g., IOI-HA-SO [40], SOS-HEAR [41])	Score on Likert Rating Scales
	Assessment of cognitive influences on speech perception	Cognitive Measures, e.g. for Working-Memory Capacity (e.g., Reading Span [38]), Executive Functioning and Attention (e.g., Stroop Task), Overall Cognitive Ability (e.g., MoCA [39])	Performance Level [%-correct responses or time-to-complete outcomes]
	Subjective Assessment of Listening Effort and Hearing Fatigue	Questionnaires about Listening Effort in Everyday Life (e.g., CTO [42]), Rating Scales of Effort perceived during above listed Audiological Tests	Score on a Continuous Rating Scale or on a Likert Rating Scale
	Objective Assessment of Listening Effort and Spare Capacity	Response Delays during above listed Speech Intelligibility Tests; Dual-Task Paradigms with Speech Intelligibility as primary task and a Cognitive Outcome Measure as the Secondary Add-On Task (e.g., Assessment of Cognitive Capacity for tasks of Selective Attention or Working Memory during the Primary Task [43, 44, 45])	SRT [%] and Errors [%] or Response Times [ms]

Table 4: Primary outcome table.

5.2 Secondary Outcomes

Product benchmark: Comparison of new Phonak Hearing Systems to previous models and to competitor devices according to primary objectives in accordance to table 4.

5.3 Other Outcomes of Interest

Other outcomes of interest are side-effects.

5.4 Safety Outcomes

N/A

6. STUDY DESIGN

(ICH/E6 6.4; AGEK 4; SPIRIT #8)

6.1 General study design and justification of design

(ICH/E6 6.4.2, 6.4.5; AGEK 4.2; SPIRIT #8)

ICH: The scientific integrity of the trial and the credibility of the data from the trial depend substantially on the trial design.

ICH: A description of the type/design of trial to be conducted (e.g., double-blind, placebo-controlled, parallel design) and a schematic diagram of trial design, procedures and stages.

ICH: The expected duration of subject participation, and a description of the sequence and duration of all trial periods, including follow-up, if any.

A methodical evaluation of new CE-Labelled Phonak Hearing Systems is intended to be conducted on hard of hearing participants to grant quality control prior to product launch in spring or in fall per year. The aim of the investigation is to continuously ensure zero-defect overall performance of the new hearing systems as well as maximum benefit for the participant with the devices in comparison to previously outstanding Phonak Hearing Systems and to equivalent strong competitor devices across 10 years (October 2015 to 2025). This will be a controlled, single blinded (participants), randomised (testing method), cross-over (investigational product) active comparator study which will be conducted mono centric at Sonova AG Headquarters based in Stäfa.

In total, a maximum of 210 adult subjects will participate per year. If necessary, there will be a pre-study with a maximum of five internal (normal hearing or hearing impaired) subjects before the main study to prove the actual study design. A pre-study will be considered if there are adjustments away from the normal audiological standard regarding the method, setup, subject group etc. If a pre-study is necessary will be decided by the principal investigator. Then, according to experience, 6 clinical trials (main studies) with a maximum of 30 subjects per study each of two months duration, are conducted for a quality control of the Phonak Hearing Systems. Typically, each participant gets a series of weekly appointments of 1.5 to 2 hours (lab trials), respectively, including the fitting procedure of the hearing system as well as the objective tests. Between the weekly appointments, the home trials take place so that the subjects can test the devices in their daily life in accordance to some questionnaires either pCRF or eCRF. In dependence on the form factor of an investigational product, which provide different gain levels, participants with appropriate hearing losses ranging from mild, moderate, severe to profound need to be recruited. Testing takes place in one of the three double-walled sound-attenuating booths (Validation Room 1, 2 and 3, see section 9.2.1).

Despite of the well-defined study protocol, some limitations of the study design are inherent. For example, it is not possible to blind the investigational product during the home trial. Especially the housing/naming of competitor devices are revealing their identity. During the lab trials, the participants are fully blinded. An additional limitation of the study design are software updates during the study for both the fitting software and the hearing systems. As soon as quality problems occur, such as acoustic feedback problems or artefacts, for example, a device deficiency form is filled in and the devices get revised leading to different firmware versions across the study which need to be considered during the data analysis.

6.2 Methods of minimising bias

(ICH/E6 6.4.3; AGEK 4.3; SPIRIT #16, 17)

ICH: A description of the measures taken to minimize/avoid bias, including: Randomization, Blinding.

In order to minimize bias:

1. Strictly defined hearing instruments settings will be taken for:
 - A. Lab Trial: All objective lab tests will be performed in a lab setting of the hearing instruments. The lab setting for each hearing instrument will be defined in appointment 1 after performing the first fit to the individual hearing loss of the subject as proposed by the Phonak Fitting Software, and, if necessary, a fine tuning only in gain level.
 - B. Home Trials: If necessary, for the Home Trials the hearing instruments will be fine-tuned based on the individual hearing loss and pre-calculation (lab setting). The fine tuning comprises every option offered in the fitting software as it can typically be applied by the hearing care professionals in the market.
2. No investigator change per subject during the study, if possible (exceptions: sickness, vacation, advanced training).
3. Uniform and extensive training of the whole study team and monitor prior to study start.
4. Use of electronic database eClinicalOS (Merge) for direct data capture by the investigators during the lab trial and by the study participants during home trial (reduction of pCRFs to the greatest possible extent).
5. Close meshed monitoring of subject appointments conducted by new investigators.
6. To avoid learning effects, subjects cannot jump from one study to the next (minimum break of six months, at least).
7. To avoid training effects, standardized test methods are applied according to their instructions.
8. Sensitizing the investigators to bias (e.g. Halo-Effects).
9. Orthogonal design of the questionnaires (p/eCRF) to fulfil the criteria for test quality (objectivity, validity, reliability).
10. Reduction of order effects – randomized order of the test procedure of the subjective judgments, the objective tests and the hardware comparisons.
11. Limited information will be given to the subjects regarding the test products and the features.
12. In order to ensure a high satisfaction of the subject, the physical position in and on the ear must be comfortable and it must be ensured that the subject can operate the device well (e.g. putting the hearing aids on, changing batteries, switching on/off). These aspects will be observed and checked throughout the study sections so that they are not the form factor to cause any bias in results, especially subjective results.

6.2.1 Randomisation

Randomization and concealment of randomization list is generated by the Principle Investigator using a script written in the program MatLab. The randomization is applied to all investigational products for both the lab trials and the home trials. Furthermore, the order of the test method used per visit is liable to a randomization.

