11.2 Determination of Sample Size

ICH: The number of subjects planned to be enrolled. In multicentre trials, the numbers of enrolled subjects projected for each trial site should be specified. Reason for choice of sample size, including reflections on (or calculations of) the power of the trial and clinical justification.

Based on numerous publications in the field of audiology research using standardized measurement methods testing hearing impaired subjects as well as on Sonova AG's extensive study experience, a number of maximum 20 subjects per study is sufficient to obtain statistically significant results on a significance level of 5%.

In the case of the pre-study a maximum of 5 subjects is included, since merely the study concept needs to be proved, and no inferential but only descriptive statistics is carried out. Later, during the main study, both descriptive and inferential statistics are executed. In the past, typically 20 subjects participated per study leading to significant results approaching the primary objective (zero-defect overall performance of the new Phonak Hearing Systems). To tackle the secondary objective (product benchmark) a number up to 30 subjects have taken part in several previous investigations. This case is founded in the fact that a study design of parallel groups, either containing 10 or 15 subjects each, is applied as soon as more than one competitor device is compared to the Phonak Hearing System. For this reason, an appropriate number of subjects will be included during the planned investigations.

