11.4 Planned Analyses

ICH: A description of the statistical methods to be employed, including timing of any planned interim analysis(es).

In a first step, the distribution of the collected subjective and objective data is verified. Based on this outcome (normally distributed yes/no) and depending on the scale level (nominal, ordinal, interval or rational) of the variables, descriptive statistics is executed in the form of determining the mean value and standard deviation or the median and quartile, respectively. Furthermore, diagrams for visualization are compiled such as boxplots, histograms and scatterplots. Then, after a determination of the measurement variables regarding their relationship or their difference, inference statistics is executed by applying the appropriate parametric or non-parametric test depending on the data's distribution either using the correlation coefficient (Pearson, Spearman), t-Test, Mann-Whitney-U-Test, or the Wilcoxon-Test. Generally, a significance level of 5% is pursued.

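### No balancing of device sequences is stated and the planned tests carry no period term, so chance imbalance in device order can reduce the precision of a single cross-over comparison

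*Combined protocol and SAP*

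**What the plan says.** Section 6.1 describes a "cross-over (investigational product) active comparator study"; the synopsis allows a cross-over or a parallel design. On how the list is built, section 6.2.1 states that "Randomization and concealment of randomization list is generated by the Principle Investigator using a script written in the program MatLab" and that "The randomization is applied to all investigational products for both the lab trials and the home trials". It also says that test order within a visit is randomised. Section 6.2 item 10 names the purpose: "Reduction of order effects – randomized order of the test procedure of the subjective judgments, the objective tests and the hardware comparisons". Section 7.3 adds only that assignment is by chance and that the first eligible volunteers are taken. Blocks, balanced sequences, strata and allocation ratio are not mentioned.

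Section 11.4 lists the t-test, Mann-Whitney, Wilcoxon and correlation coefficients, and adds: "Generally, a significance level of 5% is pursued". No model with a period or sequence term is listed. Section 11.2 regards at most 20 participants per study as enough and describes parallel groups of 10 or 15 when more than one competitor device is compared.

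The protocol does take steps against time-related effects. Section 9.2 has participants complete a training session before every measurement and leaves those data out of the analysis. Section 6.2 item 1A fixes a lab setting at the first appointment. Section 6.1 acknowledges that "the devices get revised leading to different firmware versions across the study" and says that this has to be taken into account when the data are analysed, without saying how.

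**The concern.** In a cross-over, each participant's device difference contains the period effect with a sign that depends on which device came first. With equal numbers in each sequence these contributions cancel in the mean. With unequal numbers part of the period effect remains, and the listed one-sample paired tests cannot separate it from the device difference.

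A period effect is plausible here. New and experienced hearing-aid users are both enrolled, and devices are worn at home in week-long trials between appointments. The training session addresses familiarity with a test; it does not cover getting used to amplification over weeks of wear. Each main study is reported on its own before a launch, and section 13 allows results to support product claims. A chance shift in one study is therefore not averaged away by the others. The comparison affected is the product benchmark, which is the secondary objective.

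**Working it through.** **Inputs from the protocol.** N = 20 per study (section 11.2); significance level 5%, sidedness not stated (section 11.4); cross-over in device (section 6.1); paired tests without a period term (section 11.4). The protocol gives no effect size, SD or power, so the figure of 20 cannot be reproduced. It states no imbalance probability either.

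**Assumptions.** Two devices and two sequences (AB, BA); independent 1:1 draws; an additive period effect π common to all participants, set at 0.25, 0.5 and 1 times σ, the SD of the paired difference; two-sided tests.

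**Step 1: how often the split is uneven.** The number receiving AB is Binomial(20, 0.5).

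- Exactly 10:10: C(20,10)/2^20 = 0.176
- 7:13 or worse, either way: 2 × P(X ≥ 13) = 0.263
- 6:14 or worse: 0.115
- 5:15 or worse: 0.041
- For N = 30: 11:19 or worse 0.200; 10:20 or worse 0.099

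**Step 2: how much of a period effect passes through.** With device difference τ, an AB participant contributes τ − π to A − B and a BA participant τ + π. The mean is shifted by π × (n_BA − n_AB)/N. At 7:13 this is (13 − 7)/20 = 0.30 of π; at 10:10 it is zero. As an illustration, an assumed period effect of 0.5 to 2 dB SNR would shift a speech-in-noise difference by 0.30 × 0.5 = 0.15 dB to 0.30 × 2 = 0.6 dB.

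**Step 3: type I error of the unadjusted paired t-test** (simulation, 100,000 runs, N = 20).

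| π/σ | simple randomisation, averaged | given a 7:13 split | forced 10:10 |
|---|---|---|---|
| 0.25 | 0.049 | 0.055 | 0.043 |
| 0.5 | 0.050 | 0.067 | 0.029 |
| 1 | 0.051 | 0.076 | 0.006 |

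Averaged over simple randomisation, the mean shift is zero to within simulation error and the level holds. Under forced balance the estimate is not shifted, but the period effect still inflates the estimated SD, so the test becomes conservative.

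**Step 4: cost in precision.** Over simple randomisation the variance of the unadjusted mean is (σ² + π²)/N, so it rises by π²/σ²: 0.25² = 6%, 0.5² = 25%.

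**Step 5: why both halves of the fix are needed.** With a period term the variance is σ² × N/(4 × n_AB × n_BA). At 10:10 this is σ² × 20/400 = 0.050σ². At 7:13 it is σ² × 20/(4 × 91) = 0.055σ², about 10% more. The period term removes the shift, and balance removes the remaining loss.

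**The case against.** The strongest reply is that silence is not evidence. A MatLab script can produce balanced sequences as easily as unrestricted ones, and a protocol covering about six studies a year may reasonably leave list construction to each study. That stands: a reader might infer from section 6.2.1 that order is drawn without any balancing, but the text does not say so. The 26% figure therefore holds only under simple randomisation with exactly two sequences.

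Second, randomised order already protects against systematic bias. This also stands, and the averaged column in Step 3 confirms it. A reader might infer that the planned comparison is biased or its error rate inflated. That is true only conditionally on an uneven split, and even then the type I error is 0.055 to 0.076 over the range tried.

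Third, the protocol contains countermeasures, and some of its remarks on time effects concern other things. The six-month break in section 6.2 item 6 is about learning between studies. The acclimatisation remark in section 3.7 concerns refitting after headache. Paired-comparison and MUSHRA tasks switch quickly between devices, so a period model does not fit them. This narrows the point to measures taken in successive wearing periods, mainly home-trial ratings and repeated lab tests.

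Fourth, firmware revisions are triggered by defects, arrive in calendar time and change the product itself. They are not a common period effect, and a balanced list would not cancel them. This is correct.

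Finally, the benchmark is a secondary objective, section 11.1 says that no specific hypothesis is tested, and sequence balance is irrelevant to parallel groups. These facts limit the weight of the point. They do not remove the loss of precision where a cross-over is used.

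**Conclusion.** The point holds as a minor, inexpensive improvement. For cross-over studies the protocol relies on "randomized order of the test procedure of the subjective judgments, the objective tests and the hardware comparisons" without stating that sequences are balanced, and its listed tests have no period term. Under simple randomisation of two sequences at N = 20, about one study in four would have a 7:13 or worse split. In those studies at least 30% of any additive period effect would enter the unadjusted device difference. On average the cost is lower precision: roughly 6% to 25% more variance for period effects of 0.25 to 0.5 SD.

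The number of sequences, the simple draws and the size of the period effect are assumptions, and none is in the protocol. The documents do not support the stronger conclusions that sequences are in fact unbalanced, that the device difference is systematically biased, or that balancing would deal with firmware changes. If the script already balances sequences, what remains is to say so and to add the period term.

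**What to change.** In section 6.2.1, for cross-over studies, state that the script draws device sequences from a balanced set: AB/BA for two devices, a Latin or Williams square for three or more. Use permuted blocks so that sequences are used as equally as N allows. Stratify by hearing-aid experience only where numbers permit. A three-device Williams design has six sequences, so at N = 20 exact equality is already impossible (20/6 is not a whole number), and less attainable within strata.

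A replacement participant takes the sequence of the person replaced, unless that person's complete data stay in the analysis, which sections 8.5, 11.4.1 and 11.5 allow.

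In section 11.4, specify that the device difference is analysed with a period term. For two devices this is the period-adjusted cross-over t-test, comparing within-person period differences between the two sequence groups, or Mann-Whitney on the same differences. Both are tests that the section already lists. Say separately how firmware versions enter the analysis.

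The cost is a few lines of script, a few sentences of protocol text and one degree of freedom in the two-device analysis (18 instead of 19 at N = 20). Blocks make the next sequence slightly more predictable, so block size should be withheld from the testers. No visit, device or sample size changes.

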6.2.2 Blinding procedures

Trial participants will be blinded after assignment to interventions. During the lab trials, the subjects will not know which hearing system they are wearing because the investigators will mount the hearing instruments covered to the subjects ear. During the home trials, the labelling on the housing will be covered by a sticker, if possible. Nevertheless, the brand of the device might be identified by the subjects due to the shape of the housing (limited blinding).

6.2.3 Other methods of minimising bias

To the greatest possible extent validated questionnaires (p/eCRF) come into operation. However, specifically adapted questionnaires are inevitable to validly capture the appropriate information needed.

6.3 Unblinding Procedures (Code break)

(ICH/E6 6.4.8; AGEK 4.2; SPIRIT #17b)

ICH: Maintenance of trial treatment randomization codes and procedures for breaking codes.

A subject coding list is safely stored and can be used to break the code, if necessary. Also the randomization lists can be used to identify the subject and his specific measurement order, if applicable.

7. STUDY POPULATION

(ICH/E6 6.2.6, 6.4.6; AGEK 3.2, 5; SPIRIT #9, 10, 15, 16, 21)

ICH: Description of the population to be studied.

This section describes the population to be studied.

7.1 Eligibility criteria

(ClinO, Art 25d5; ICH/E6 6.5.1&6.5.2; AGEK 5.2&5.3; SPIRIT #10)

ICH: Subject inclusion and exclusion criteria.

Only adult subjects will participate. In the pre-study normal hearing persons as well as hearing impaired persons will participate whereas in the main study merely hearing impaired subjects will be involved.

Participants fulfilling all of the following inclusion criteria are eligible for the study:

- Adult (minimum age: 18 years) hearing impaired persons both with and without (experience with) hearing aids
- Good written and spoken (Swiss) German language skills
- Healthy outer ear (without previous surgical procedures)
- Ability to fill in a questionnaire (p/eCRF) conscientiously
- Informed Consent as documented by signature

The presence of any one of the following exclusion criteria will lead to exclusion of the participant:

- Contraindications to the MD in this study, e.g. known hypersensitivity or allergy to the investigational product
- Limited mobility and not in the position to attend weekly appointments
- Limited ability to describe listening impressions/experiences and the use of the hearing aid
- Inability to produce a reliable hearing test result

- Massively limited dexterity
- Known psychological problems
- Central hearing disorders

